5.3. Referral procedures

All SAEs should be reported to the Research Ethics Committee where in the opinion of the Chief Investigator the event was:

- 'related', i.e. resulted from the administration of any of the research procedures; and
- 'unexpected', i.e. an event that is not listed in the protocol as an expected occurrence.

Reports of related and unexpected SAEs should be submitted within 15 days of the Chief Investigator becoming aware of the event, using the NRES SAE form.

Local investigators should report any SAEs to the sponsor and their Local Research Ethics Committee and/or Research and Development Office.

**Contact details for reporting SAEs, for attention of
[name] [name] –
[contact] [contact]
Email: [contact]
(Mon to Fri 09.00- 17.00)**

6. STATISTICS AND DATA ANALYSIS

The statistical power calculation is based on BP-lowering effects ($-7.6 \pm 1.4 / -5.3 \pm 1.4$ mmHg) of a DASH fruit and vegetable diet (+4.5 servings/day) vs average US diet in 15 obese hypertensive participants with an average BP of 136/90 mmHg in a 3-wk cross-over study with nutritional advice (no controlled diet).³³ Assuming a conservative detectable effect size (-1 mmHg SBP) considering differences in design and type of participants, 18 participants would be sufficient to detect a difference of 1 mmHg in SBP between groups (two-sided test at 5%, SD SBP change of 1.4 mmHg, 80% power). As we use block randomisation with 6 intervention sequences, internal independent statisticians have advised to randomise a substantial number of participants per sequences. To further strengthen the study design, we will recruit and randomise (stratified by gender) 36 participants in total – with 6 participants in each group.

Treatment effects will be calculated as the changes between values at start and end of each intervention sequence. Treatment effects will be tested by comparing changes of each of the increased fruit and vegetable interventions with changes during low fruit and vegetable period (control group), and of the citrus fruit and cruciferous vegetables period with increased commonly consumed fruit and vegetable intervention. Linear mixed models will be used for repeated measures to compare changes. Treatment and period will be set as fixed effects and subject as random effect. To test for carryover effect, the previous treatment will be included in the model. Statistical significance will be set at 2-sided P-value of 0.05. The researcher performing the statistical analyses will be blinded to the treatment groups.

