2.2 Rationale of current study

Low fruit and vegetable consumption have been identified as major risk factors contributing to hypertension and CVD. Meta-analyses of prospective cohort studies showed strong evidence that eating higher amounts of fruit and vegetables lowers the risk of CVD by ~20% in a dose-response manner.⁵⁻⁸ Two landmark large intervention studies demonstrated that untreated mildly hypertensive participants who increased their daily fruit and vegetable intakes significantly reduced their average systolic BP by 2.8 mmHg systolic and diastolic by 1.1 mmHg compared to the control group with average US diet, with stronger BP-lowering effects in hypertensive participants.^{1,9} These findings underlie the evidence of the current dietary recommendations to eat at least 5 (80 gram) portions of a variety of fruits and vegetables per day with a limit of 150 ml 100% pure, unsweetened juice counting as one portion.

Fruits and vegetables are however biologically and chemically complex and vary largely in amounts and types of nutrients and bioactive compounds. Prospective cohort studies have only since 2010 started to investigate the influence of eating higher amount of specific types of fruits and vegetables on the risk of CVD. Meta-analyses of prospective cohort studies indicate that higher intakes of apples and pears, citrus fruits, carrots, cruciferous vegetables (e.g. broccoli and cabbage), grapes, green leafy vegetables, raw vegetables, and tomatoes have been suggested to lower the risk of CVD by 14-22%.⁸ Few cross-sectional¹⁰ and prospective cohort studies^{11,12} have been published on associations of types of fruits and vegetables with BP or risk of hypertension, with inconsistent findings.

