Using metabolomic strategies, small, short-term intervention studies have identified potential biomarkers for citrus fruits (proline betaine) and broccoli (S-methyl-L-cysteine sulfoxide (SMSCO)) in healthy participants.^{20,21} In a large-scale epidemiologic cohort study, the PI investigated their validity by combined analyses from high quality dietary data (24-hour dietary recalls), measured BP data and 24-hr urine collections measured by NMR spectroscopy from 2,032 US and 449 UK participants. In both populations and across clinic visits, consistent and strong correlations were found for intakes of citrus fruit with proline betaine (0.72), 4-hydroxyproline betaine (0.63) and several co-metabolites (0.22-0.49) related to the same metabolic pathway and for cruciferous vegetables with S-methyl-L-cysteine sulfoxide (SMSCO, 0.39). These biomarkers will be highly valuable as objective assessment of citrus fruits and cruciferous vegetable intake, as unbiased estimates of associations with disease outcomes in large-scale epidemiological studies, and as objective measures of compliance in intervention studies.

Although meta-analyses of prospective cohort studies indicate that higher intakes of citrus fruits and cruciferous vegetables lower the risk of CVD⁸, limited evidence exists from intervention studies. Few small, acute interventions showed inconsistent findings on BP and endothelial function after supplementation of flavanones and/or orange juice²⁵⁻²⁷, while little evidence exists on cardioprotective effects of cruciferous vegetables.²⁸⁻³⁰ Based on the evidence from prospective cohort studies and recent identification of strong, specific, and validated urinary markers for these metabolites, we will test increased intakes of citrus fruits and cruciferous vegetables on vascular function in this intervention study as proof of concept to develop future, larger intervention studies. We will not only test increased intakes of citrus fruit and cruciferous vegetables against low fruit and vegetable consumption, but also against increased intakes of other fruits and vegetables to rule out the effect of the higher amount consumed.

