3.1 Study objectives and outcome measures

To assess the effect of types of plant foods on vascular function in untreated prehypertensive participants.

Primary outcome

Changes in systolic and diastolic blood pressure (mmHg) measured by automated oscillometric device (average of 3 measurements).

Secondary outcomes

Changes (end minus baseline values) in:

1. Arterial stiffness assessed by pulse wave velocity and pulse wave analysis
2. Cardiovascular risk factors measured in fasted plasma samples:

- a. Lipid profiles: total cholesterol, high-density lipoprotein cholesterol, triacylglycerides (low-density lipoprotein cholesterol will be calculated using the Friedewald formula)
- b. Insulin resistance: glucose, insulin, HbA_{1c} (HOMA-IR will be calculated using fasting glucose and insulin values)
3. Markers of endothelial function measured in fasted plasma samples (e.g. C-reactive protein)
4. Markers of low-grade inflammation measured in fasted plasma samples (e.g. Interleukin-6)
5. Urinary and circulatory metabolite profiles and individual metabolite levels
6. Established objective urinary and circulatory markers of food intake:
 - a. Fruits and vegetables: vitamin C, carotenoids, potassium, nitrate
 - b. Salt: sodium
 - c. Protein and muscle mass turnover: urea nitrogen and creatinine
7. Composition of gut microbiota to be measured from stool samples
8. Cognitive function measured by six computerised cognitive tests to assess four main cognitive domains: memory, processing speed, attention, and executive function
9. Self-rated general health and mental well-being
10. Average total, daytime, night time 24-hr ambulatory blood pressure (in subsample)
11. Average objective physical activity intensity and sleep time (in subsample)

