3.1 Confidence intervals and p-values

95% confidence intervals will be reported for the intervention effects on all outcomes. p-values will only be reported for the primary outcomes. Because this is a pilot study, no adjustment for multiple comparisons will be made.

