5.2 Analysis methods

For each outcome variable, the mean and SD of the variable at each study timepoint will be reported, i.e. randomisation (visit 1), start of first intervention period (visit 2), end of first intervention period (visit 3), start of second intervention period (visit 4), end of second intervention period (visit 5), start of third intervention period (visit 6), end of third intervention period (visit 7). The mean and SD of the change in each outcome variable from the start to the end of each intervention period will also be reported.

A linear mixed effects regression model will be used to estimate the effect of each of the 2 dietary interventions with the control group and its confidence interval. Intervention group and period will be included in the model as fixed effects, and the individual identifier as the random effect. The outcome variable in the model will be the relevant measure at the end of each intervention period. This is consistent with CONSORT recommendations¹ that discourage use of change scores, and also with recommendations by Fleiss et al² and Willan and Pater³ that adjustment for baseline values of the outcome should be avoided in crossover trials.

The model assumes that the residuals, conditional on the random effect, are normally distributed. This assumption will be assessed graphically for each outcome, and if not satisfied, an appropriate transformation (e.g. log- or rank-based inverse normal transformation) for that outcome will be considered.

The model assumes that missing values are missing at random.

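### The power calculation uses an unlabelled ±1.4 mmHg as an SD; it is most plausibly a standard error, and if so power for 1 mmHg is about 11% at 18 participants and 19% at 36, not 80% or more

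*Protocol*

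**What the plan says.** Protocol section 6 bases the sample size on a published effect of −7.6 ± 1.4 mmHg systolic and −5.3 ± 1.4 mmHg diastolic for a fruit and vegetable diet against an average US diet, "in 15 obese hypertensive participants with an average BP of 136/90 mmHg in a 3-wk cross-over study with nutritional advice (no controlled diet"). It does not say what the ± denotes. The next sentence sets a target of 1 mmHg systolic and concludes that "18 participants would be sufficient to detect a difference of 1 mmHg in SBP between groups", with the settings "two-sided test at 5%, SD SBP change of 1.4 mmHg, 80% power". Recruitment is then raised to 36, six per sequence. The reasons given are the number per sequence and a stronger design, not a different SD.

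The SAP has no sample-size section and does not revisit the figure. It says that "95% confidence intervals will be reported for the intervention effects on all outcomes". For the model, "The outcome variable in the model will be the relevant measure at the end of each intervention period".

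Protocol section 2.2 cites two large trials in which participants eating more fruit and vegetables "significantly reduced their average systolic BP by 2.8 mmHg systolic and diastolic by 1.1 mmHg compared to the control group". It presents the present trial "in this intervention study as proof of concept to develop future, larger intervention studies".

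**The concern.** The same 1.4 appears first as an unlabelled ± attached to a mean effect and then, one sentence later, as an SD. A ± next to a mean can be either an SD or a standard error. With 15 people the two differ by a factor of √15 = 3.9, and the required sample size by a factor of about 15. The value is very small for the SD of a within-person difference in systolic pressure between two diets, and it is ordinary for a standard error.

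This is the only statement in either document of what the trial can detect. If the input is wrong, a null result could be misread as excluding a 1 mmHg effect. A later trial planned from the same figure would also be far too small.

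**Working it through.** **Inputs.** From Protocol section 6: difference to detect 1 mmHg; two-sided 5%; SD entered 1.4 mmHg; target power 80%; source effect −7.6 ± 1.4 (systolic) and −5.3 ± 1.4 (diastolic) in n = 15; calculated n = 18; planned n = 36. From Protocol section 2.2: effects of 2.8 mmHg systolic and 1.1 mmHg diastolic.

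**Method.** Paired t-test, exact power from the noncentral t distribution with n − 1 degrees of freedom and noncentrality δ√n / SD.

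**1. Reproduce the plan's figure.** With δ = 1 and SD = 1.4, power is 79.0% at n = 17 and 81.5% at n = 18, so 18 is the smallest n reaching 80%. At n = 36 power is 98.6%. A parallel-group calculation gives 31 per arm, and treating 1.4 as a per-period SD (SD of the difference 1.4√2) gives 52% at n = 18. So the plan's 18 treats 1.4 as the SD of the within-person difference between two diets.

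**2. Is 1.4 credible as that SD?**
- Systolic t = 7.6 / (1.4/√15) = 21.0. Diastolic t = 5.3 / (1.4/√15) = 14.7. Both come from 15 people on advice alone.
- About 95% of individual systolic falls would lie in 7.6 ± 1.96 × 1.4, that is 4.9 to 10.3 mmHg.
- A difference between two visits has variance of at least 2σ², where σ is the per-visit SD, so σ ≤ 1.4/√2 = 0.99 mmHg even if everyone responds identically to diet. If the difference is between two change scores (four visits, the analysis in Protocol section 6), σ ≤ 1.4/2 = 0.70 mmHg. In this trial systolic pressure is "measured by automated oscillometric device (average of 3 measurements").
- Read as a standard error, the same figures give t = 7.6/1.4 = 5.4 and 5.3/1.4 = 3.8.

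**3. Consequence if ± is a standard error.** SD = 1.4 × √15 = 5.42 mmHg.

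| Quantity | SD 1.4 | SD 5.42 |
|---|---|---|
| Power for 1 mmHg, n = 18 | 81% | 11% |
| Power for 1 mmHg, n = 36 | 99% | 19% |
| n for 80% power at 1 mmHg | 18 | 233 |
| Expected 95% CI half-width, n = 36 (2.03 × SD/6) | 0.5 mmHg | 1.8 mmHg |

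At n = 36 and SD 5.42, power is 58% for 2 mmHg, 85% for 2.8 mmHg and 90% for 3 mmHg. The difference detectable at 80% power is 2.6 mmHg.

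**4. Range over assumed SDs, n = 36.**

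| SD (mmHg) | Power for 1 mmHg | Power for 2.8 mmHg | Detectable at 80% (mmHg) |
|---|---|---|---|
| 4 | 31% | 98% | 1.9 |
| 5 | 22% | 90% | 2.4 |
| 6 | 16% | 78% | 2.9 |
| 7 | 13% | 65% | 3.4 |
| 8 | 11% | 53% | 3.8 |

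For smaller SDs, power for 1 mmHg at n = 36 is 83% at SD 2 and 49% at SD 3. The largest SD that still gives 80% power for 1 mmHg is 1.43 mmHg at n = 18 and 2.08 mmHg at n = 36.

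**5. Check against the planned model.** A three-period mixed model with 36 complete participants has 108 − 36 − 2 − 2 = 68 residual degrees of freedom. At SD 5.42 this gives 19% power for 1 mmHg, 86% for 2.8 mmHg and a detectable difference of 2.57 mmHg. The paired-t figures stand.

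**The case against.** - **The label.** The protocol does call 1.4 an SD, and its authors had the source, which this review does not. If they are right, power is 81% at 18 and 99% at 36. This stands, and it is why every figure at SD 5.4 is conditional. The ± might also be something else, such as a model-based standard error or a confidence half-width, in which case 1.4 × √15 would not be exact. The range over SDs allows for this.
- **Plausibility is not proof.** The documents give no visit-to-visit SD for comparison, and they do not say how pressure was measured in the source study. That is true, but t = 21 follows from the protocol's own numbers, and nothing else in either document supports so small an SD.
- **Slack.** Recruiting 36 rather than 18 protects the claim up to an SD of 2.08, about 50% above 1.4. That does not reach the standard-error reading.
- **Limited harm.** The trial is a pilot. The SAP refers to participants whose sequences were mixed up, so randomisation has already happened, and no estimate or decision rule in the SAP uses 1.4 or 1 mmHg. SAP section 5.2 commits to reporting SDs by visit and of within-period changes, so a follow-on trial would have its own variability data, and the confidence intervals would show the imprecision. These points reduce the harm but do not make the planning statement correct.
- **Diastolic pressure.** It is also a primary outcome and carries the same ±1.4. Under the standard-error reading, power at 36 for the cited 1.1 mmHg effect is about 22%. The restated text should not imply that both primary outcomes are covered.

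**Conclusion.** The concern holds. There is no arithmetic slip; the fault is an unverified input that the protocol's own figures make implausible. If ±1.4 is a standard error from 15 people, the SD is about 5.4 mmHg and power for 1 mmHg is about 11% at 18 participants and 19% at 36. A 1 mmHg target would then need about 233 people.

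The trial is not thereby uninformative: at SD 5.4, 36 participants have about 85% power for the 2.8 mmHg systolic effect cited in Protocol section 2.2.

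Two assumptions remain. The first is that the ± is a standard error, which only the source can confirm. The second is that the SD of the source study's between-diet difference carries over to the end-of-period difference that the SAP analyses. Confidence in the standard-error reading is medium. The need to resolve the label before the calculation is relied on or reported does not depend on it.

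**What to change.** Check in the cited source whether ±1.4 is an SD or a standard error.

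If it is a standard error, delete the claim that 18 participants can detect 1 mmHg and state for the planned 36:

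> Reading ±1.4 as a standard error (n = 15), the SD of the within-person between-diet difference in systolic pressure is about 5.4 mmHg, and 36 participants give 80% power for about 2.6 mmHg (1.9 to 3.8 mmHg for assumed SDs of 4 to 8). This SD is assumed to apply to the end-of-period between-diet difference analysed in the SAP.

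Add a corresponding line for diastolic pressure, or say that the calculation covers systolic pressure only.

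If the source shows an SD, label it as the SD of the between-diet difference and explain why so small a value is expected here.

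The cost is one look at the source and a change of wording, with no added participants and no change to the analysis. If the standard-error reading is confirmed, the stated detectable difference becomes less favourable, about 2.6 mmHg instead of 1 mmHg.

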7. REGULATORY ISSUES

ETHICS APPROVAL

This study has been ethically approved by the London Brent Research Ethics Committee (17/LO/0862). The study will be conducted in accordance with the recommendations for physicians involved in research on human subjects adopted by the 18th World Medical Assembly, Helsinki 1964 and later revisions. Amendments to the protocol should be approved by the sponsor before being sent to ethics. After ethical approval, all amendments must have Trust R&D approval before they can be implemented.

CONSENT

Consent to enter the study must be sought from each participant only after a full explanation has been given, an information leaflet offered, and time allowed for consideration. Signed participant consent should be obtained. The right of the participant to refuse to participate without giving reasons must be respected. After the participant has entered the study the clinician remains free to give alternative treatment to that specified in the protocol at any stage if he/she feels it is in the participant's best interest, but the reasons for doing so should be recorded. In such cases, the participants remain within the study for the purposes of follow-up and data analyses. All participants are free to withdraw at any time from the study without giving reasons and without prejudicing further treatment.

CONFIDENTIALITY

The Chief Investigator will preserve the confidentiality of participants in the study and is registered under the Data Protection Act.

INDEMNITY

The University of Cambridge holds adequate provision for insurance or indemnity to cover liabilities which may arise in relation to the design, management and conduct of the research project.

SPONSOR

The University of Cambridge will act as the main sponsor for this study.

FUNDING

This research project is funded by the Academy of Medical Sciences. Travel expenses on public transport to and from the Cambridge Epidemiology & Clinical Trials Unit testing sites will be reimbursed up to a maximum of £20 per day for all visits (including screening visit) for both eligible and non-eligible volunteers. There will be no additional reimbursement during the intervention, however all meals and snacks during the 9 week intervention will be provided by the research team and delivered at participant's home.

AUDITS AND INSPECTIONS

The study may be subject to inspection and audit by The University of Cambridge under their remit as sponsor and other regulatory bodies to ensure adherence to GCP and the NHS Research Governance Framework for Health and Social Care (2nd edition).

8. STUDY MANAGEMENT

The day to day management of the study will be co-ordinated by [name] [name].

9. PUBLICATION POLICY

The findings of the research will be published in peer-reviewed journals and will be presented at targeted academic meetings to ensure wide reach of the results. In addition, we will be collaborating with patient groups and professional groups to disseminate the findings via multiple media channels such as patient association publications, print and broadcast media.

Statistical Analysis Plan

The effects of types of fruits and vegetables on vascular function in prehypertensive participants: a pilot study

[figure not shown]
[figure not shown]
SAP revision history

Date	Version	Justification for SAP version
24 Jan 2022	1.1	Initial draft.
04 Feb 2022	1.2	For review.
04 Mar 2022	1.3	No comments received during review. Version for sign off

SAP responsibilities

Role in SAP development	Name	Role in trial
SAP author	[name]	Study statistician
SAP reviewer 1	[name]	Overseeing statistician
SAP reviewer 2	[name]	Principal Investigator
SAP reviewer 3	[name]	Co-Investigator
SAP reviewer 4	[name]	Co-Investigator
SAP reviewer 5	[name]	Co-Investigator
SAP reviewer 6	[name]	Co-Investigator

SAP signatures

Role	Name, affiliation	Date	Signature
Trial PI	[name]	4/3/2022	
SAP author	[name]	4/3/2022	
Overseeing statistician	[name]	4/3/2022	

1 Introduction

This document describes the primary and secondary analyses of data from a pilot study whose aim is to evaluate the effects of increased intakes of citrus fruits and cruciferous vegetables on vascular function in untreated, prehypertensive participants.

Following completion of the main trial analyses described here, further exploratory analyses of the data from this study may also be conducted. These are not part of this analysis plan.

2 Study design

See Protocol – Section 3.

ClinicalTrials.gov Identifier: NCT03410342

3 Statistical principles

3.1 Confidence intervals and p-values

95% confidence intervals will be reported for the intervention effects on all outcomes. p-values will only be reported for the primary outcomes. Because this is a pilot study, no adjustment for multiple comparisons will be made.

3.2 Adherence and protocol deviations

Adherence to the intervention diets will be analysed using completed daily food checklists.

3.3 Analysis populations

The analysis population will include all participants who have study baseline measures and an outcome measure at the end of at least 1 of the intervention periods.

4 Trial population

